## 8 Schedule of Patient Activities

Scheduled evaluations after screening may be performed  $\pm 1$  day from the targeted date through Day 29; unless otherwise noted. A disease reassessment will occur between Days 21 and 42. A  $\pm 7$  day window is permitted for the end of treatment (EOT) visit. If a patient discontinues treatment before receiving all 3 blocks, subsequent time points are adjusted to maintain timing (i.e. Day 22 is moved to 1 week after the start of the last block).

In addition, targeted days may be altered as clinically appropriate. Follow-up visits are per standard of care with disease status and survival status abstracted from the medical record.

## 8.1 Required Standard of Care

Standard of care procedures should be followed for all enrolled patients, including those who are enrolled for retreatment.

Activity	Screening within 30 days of enrollment (within 14 days if for eligibility)	Day 1, Day 8, and Day 15 (start of treatment block)	Daily during infusions (i.e. Day 2-5, 9 12, 16-19)	Day 22	Day 29	Anytime between Day 21 through Day 42	End of Treatment Visit Day 60 (±7 days)	FU for overall survival (through Month 6)
consent	X							
baseline assessment	X							
medical history	X	X		X	X		X	
concomitant meds 	X	X	X	X	X		X	
physical exam	X	X		X	X		X	
vital signs including pulse oximetry	X	X	per Section 7.1.1	X	X		X	
neurologic assessment		X 		X				
provider assessment			X					
survival status							X 	X
assessment of toxicity		X	X	X	X		X	
Karnofsky PS	X				X		X	
height	X							
weight		X (- 5 days)						
CBC/diff/plt	X	X	X	X	X		X	
basic metabolic panel			X					
comprehensive metabolic panel  , magnesium and phosphorus	X	X		X	X		X	
ALT, AST, total bili, albumin 			2 times					
hepatitis B and C screening	X							
INR 	X							
eGFR	X							
Serum pregnancy test for FOCBP within 7 days of treatment start	X							
Disease assessment	X					X		
BM biopsy 	X					X		
Electrocardiogram	X							
Echocardiogram, cardiac MRI or MUGA	X							
Chest/abdomen CT	X							
assessment of response						X		X 

1 - sample to TTL per [Section 8.2](#) at time of each SOC bone marrow biopsy

2 - Neurological assessment daily including basic motor (gait), coordination (steadiness) and cognitive function (alert and oriented) - any abnormalities should be followed up with a detailed neurologic exam.

3 - Albumin, alkaline phosphatase, ALT, AST, bilirubin (total), calcium, chloride, CO2, creatinine, glucose, potassium, protein (total), sodium, urea nitrogen

4 - perform LFTs and albumin twice more during infusion week (in addition to Day of infusion start CMP) = three times during infusion week

5 - survival status at Day 60 for early study stopping rule for expansion component only

6 - until relapse/progression or start of a new therapy, then survival only

7 - document all concomitant medications, including start and stop dates, relative to administration of GTB-3550 TriKE

8- Measure and report prior to commencement of GTB-3550 therapy for information only and not as criteria for inclusion.

## 8.2 Research Related Testing, Assessments, and Sample Collections

Sample collections and other procedures after the end of the infusions will coincide with outpatient clinic visits which may not occur on the targeted day.

	Screen/ Baseline	Pre Dose 1 each Block (Day 1, 8, 15)	Daily during infusions (i.e. Day 2-5, 9-12, 16- 19)	PK/PD sampling at end of each infusion block	Day 22	Day 29	Day of SOC Disease Reassessmen t (Day 21 – Day 42)		
Toxicity Assessment			Refer to Section 10.2 for details						
Assessment for dose limiting toxicity			By Day 29 – report as DLT for Phase I only; however any patient experiencing a DLT is not eligible to continue treatment per Section 7.5						
Assessment for stopping rules			Expansion component only through Day 42 for non-hematologic, non-relapse, non- infectious toxicity (except fever), Day 60 for TRM,						
Monitoring for signs of immune activation			Pre and during TriKE infusions – all patients						
CRP, ferritin 	X	X	X (Day 5 only)						
Pulmonary Function Testing	X								
EKG		X (At 4 hours (±15 min) into the infusion)	X (at 4 hours (±15 min) into each daily infusion and at 4 hours (±15 min) after disconnect at block end)						
T Cell Subset Extended Profile 	X								
5 - 10 ml green top tubes and 1- 10 ml red top tube	X	X	X (Day 3, 10, and 17, only) 		X	X	X 		
antibody testing (sample obtained from the 10 ml red top collected in previous row)	X 	X (Day 15 only)			X	X	X 		
5 ml red top for each PK/PD time point		X	X	X 					
30 ml or as much as able to obtain of heparinized bone marrow aspirate at time of SOC bm bx	X 						X 		
Pre- and Post-TriKE drug product concentrations levels samples – each drug bag during Week 1 only									
TriKE pre-infusion sample - 2 ml of drug split between two pre- labeled 1.8 ml cryo-vials		Each drug bag during Week 1 only per Section 9.6 – collected after drug preparation is complete and before bag sent to floor, – keep refrigerated until pick-up							
TriKE post-infusion sample collection ~2 ml of drug split between two pre-labeled 1.8 ml cryo- vials		Each drug bag during Week 1 only – per Section 7.1 after infusion end and prior to discarding bag and tubing - keep refrigerated until samples are collected							

1. PK/PD time points in association with the end of each infusion block (i.e. Day 5, 12, and 19 or at the discontinuation of the block's infusions, if prior to 96 hours) - 1 hour post (±5 min), 2 hours post (±10 min), 3 hours post (±10 min), 4 hours post (±10 min) and optional 10 hours (±30 min)
2. Antibody testing will not be performed in real time nor affect a patient's initial eligibility or ongoing treatment
3. Baseline sample if feasible (repeat marrow is not required solely for research sample)

4. To Institution's clinical lab, charge to research
5. A +2 day window is permitted for this time point (Day 3 (window of days 3- 5), Day 10 (window of days 10-12) and Day 17 (window of days 17-19)
6. At time of post-treatment bone marrow biopsy or at Day 60 (End of Treatment visit)

**For UMN patients:** All samples unless otherwise noted go to Masonic Cancer Center Translational Therapy Laboratory (TTL) - Call [REDACTED] for sample pick-up.

**For non-University of Minnesota sites:**

- The 5 green top and 1 red top samples are shipped the day of collection (Monday-Thursday) for next day delivery to the Masonic Cancer Center's Translational Therapy Lab (MCC TTL).
- PK/PD samples are stored frozen and batched shipped to MCC TTL at the end of the patient's treatment.
- TriKE pre and post infusion samples (Week 1 only) are stored frozen and batch shipped to MCC TTL during Week 2.
- Bone marrow aspirate is collected at the time of standard of care bone marrow prior to treatment start and at the time of the post-treatment bone marrow biopsy. Ship day of collection to MCC TTL.

Refer to the Laboratory Manual for additional details.

It is recognized that with novel therapies as used in this study, the timing of protocol directed research samples may miss important patient specific events. For this reason, additional sets of research samples may be drawn at up to 3 time points that are not specified above.

Note: if a patient is not abiding by the standard of care study calendar ([Section 8.1](#)), collection of the research related samples (and targeted toxicities) may be altered or discontinued on an individual patient basis, as appropriate.

### 8.3 Re-Treatment Research Related Testing, Assessments, and Sample Collections

All standard of care procedures described in [Section 8.1](#) are also required for retreatment. Sample collections and other procedures after the end of the infusions will coincide with outpatient clinic visits (and may not occur on the targeted day).

	Screen/ Baseline	Block 1 only		Pre and during TriKE infusions	Day 22 or 1 week after the start of the last block	Day of SOC Disease Reassessment (Day 21 – Day 42)	
		Pre Dose 1	Day 5				
Toxicity Assessment				Refer to Section 10.2 for details			
Monitoring for signs of immune activation				Pre and during TriKE infusions – all patients			
CRP, ferritin 	X	X	X				
Pulmonary Function Testing	X						
T Cell Subset Extended Profile 	X						
5 - 10 ml green top tubes and 1- 10 ml red top tube		X			X		
antibody testing 5 ml red top tube (sample obtained from the 10 ml red top collected in previous row)	X 				X		
30 ml or as much as able to obtain of heparinized bone marrow aspirate at time of SOC bm bx	X 					X	

1- To Institutional Lab, but charge to research

2- Antibody testing will not be performed in real time nor affect a patient's initial eligibility or ongoing treatment

3- May be same sample as reassessment from 1st treatment course

For UMN patients, all samples unless otherwise noted go to Masonic Cancer Center Translational Therapy Laboratory (TTL) - Call [REDACTED] for sample pick-up.

For non-University of Minnesota sites, refer to [Section 8.2](#) for shipping information.

All “rules” of sample collection found in [Section 8.2](#) also apply to the re-treatment research samples (i.e., windows, missed samples, extra samples).

#### 8.4 Overview of Planned Correlative Studies

A number of correlative studies are performed to understand the safety and ability of the GTB-3550 TriKE to activate the immune response. Immune monitoring is a critical component of the GTB-3550 TriKE clinical trial to understand the drug pharmacokinetic/pharmacodynamic (PK/PD), its in vivo functional activity and clinical tolerance.

1. PK sampling to determine TriKE levels and secondary cytokines. In association with each TriKE treatment block, TriKE concentrations will be determined at multiple time points by standard IL-15 ELISA to detect the IL-15 linker in the TriKE as we have already validated. Samples will also be contract tested for IFN $\alpha$ , IL-6, IL-10 and TNF (and other inflammatory cytokines determined informative). This will allow us to determine drug PK/PD and immediate secondary cytokine responses in vivo.
2. Determine the absolute number and proportion of NK cells, T cells and their subsets. We have designed multi-color flow cytometry panels to look at basic lymphocytes in whole blood as well as in more detail on ficolled mononuclear cells to determine lymphocyte (and subset) proliferation as measured by Ki-67, inhibitory cells [Treg and CD33+ myeloid-derived suppressor cells] and a number of established NK cell subsets defining adaptive or conventional NK cells.
3. NK cell function induced by GTB-3550 TriKE. CD107A degranulation and cytokine production against K562 (to measure natural cytotoxicity) and CD33+ HL60 targets ( $\pm$  exogenous TriKE) will be performed.
4. [REDACTED]
5. Pre- and Post- TriKE drug product concentrations levels samples will be stored in TTL frozen at  $< -70^{\circ}\text{C}$  for future batch testing.

The marrow will be used in the research lab to study CD33 expression and targeting by allogeneic and autologous lymphocytes.

## **9 GTB-3550 TriKE Description, Supply, Preparation, and Potential Toxicities**

### **9.1 Product Description**

[REDACTED]

[REDACTED]

### **9.2 Product Manufacturing**

[REDACTED]

[REDACTED]

### **9.3 Product Formulation**

[REDACTED]

### **9.4 How Supplied**

[REDACTED]

[REDACTED]

## 9.5 Study Site Storage and Product Stability

For more information, contact the Office of the Vice President for Research and the Office of the Vice President for Student Affairs.

For more information, contact the Office of the Vice President for Research and the Office of the Vice President for Student Affairs.

## 9.6 Preparation and Administration

For more information, contact the Office of the Vice President for Research and the Office of the Vice President for Student Affairs.

the *Journal of the American Statistical Association* (1980, 75, 311-322) and the *Journal of the Royal Statistical Society, Series B* (1981, 43, 1-37). The latter paper is the most comprehensive treatment of the topic, and it is the source of the following summary. The *Journal of the Royal Statistical Society, Series B* paper is available online at <http://www.jstor.org>.

1

© 2019 Pearson Education, Inc.

- [REDACTED]
- [REDACTED]
- [REDACTED]
- [REDACTED]

## 9.7 Potential Toxicities

Although blinatumomab, a bi-specific T cell engager (BiTE), is conceptually similar to our NK cell GTB-3550 TriKE, there are important differences. Blinatumomab's toxicity is presumed related to the anti-CD3 moiety that acts as a potent stimulus for CD3+ T cells. The TriKE is different since the anti-CD16 moiety does not deliver a proliferative stimulus and in fact, we do not expect that promotion of an immune synapse alone will lead to toxicity much like natural engagement of CD16 by FDA-approved monoclonal antibodies such as trastuzumab or rituximab. Instead, we expect the toxicities of GTB-3550 TriKE may be similar to those seen with blinatumomab and/or IL-15. Other than the intramural center at the NCI in Washington DC, we probably have the most experience administering IL-15 to patients as a single agent and in combination with chemotherapy and NK cells.

[REDACTED]

Most of the side effects of IL-15 are related to immune activation including fevers, chills and some degree of immune activation. We have a prospective plan to monitor patients for these immune side effects to characterize the safety profile of the TriKE. In addition, we will use fever and tachycardia as validated clinical markers to measure early signs of immune activation to modify our dose escalation plan if needed.

## 10 Event Monitoring, Documentation and Reporting

Toxicity and adverse events will be classified according to NCI's Common Terminology Criteria for Adverse Events version 5 (CTCAE v5). A copy of the CTCAE can be downloaded from the CTEP home page at [https://ctep.cancer.gov/protocoldevelopment/electronic\\_applications/docs/CTCAE\\_v5\\_Quick\\_Reference\\_5x7.pdf](https://ctep.cancer.gov/protocoldevelopment/electronic_applications/docs/CTCAE_v5_Quick_Reference_5x7.pdf)

An exception to the use of CTCAE will be for the assessment of cytokine release syndrome (CRS). Individual adverse events which are associated with CRS will be graded per CTCAE; however the ultimate assessment will be made using a revised grading system for CRS as presented by Lee et al.

CRS Revised Grading System (replaces CTCAE v4 CRS grading)	
Grade	Toxicity Description
Grade 1	Symptoms are not life threatening and require symptomatic treatment only, e.g., fever, nausea, fatigue, headache, myalgias, malaise
Grade 2	Symptoms require and respond to moderate intervention - Oxygen requirement < 40% or Hypotension responsive to fluids or low dose of one vasopressor or Grade 2 organ toxicity
Grade 3	Grade 3 Symptoms require and respond to aggressive intervention - Oxygen requirement ≥40% or Hypotension requiring high dose or multiple vasopressors or Grade 3 organ toxicity or grade 4 transaminitis
Grade 4	Life-threatening symptoms - Requirement for ventilator support or Grade 4 organ toxicity (excluding transaminitis)
Grade 5	Death

Grades 2-4 refer to CTCAE v4.0 grading.

### 10.1 Definitions

The following definitions are based on the Code of Federal Regulations Title 21 Part 312.32 (21CFR312.32(a)).

**Adverse Event:** Any untoward medical occurrence associated with the use of a drug in humans, whether or not considered drug related.

**Suspected Adverse Reaction:** Any adverse event for which there is a reasonable possibility that the drug caused the adverse event. For the purposes of IND safety reporting, "reasonable possibility" means there is evidence to suggest a causal relationship between the drug and the adverse event. Suspected adverse reaction implies a lesser degree of certainty about causality than adverse reaction, which means any adverse event caused by a drug.

**Life-Threatening Adverse Event Or Life-Threatening Suspected Adverse Reaction:** An adverse event or suspected adverse reaction is considered "life-threatening" if, in the view of either the investigator or sponsor, its occurrence places the patient or subject at immediate risk of death. It does not include an

adverse event or suspected adverse reaction that, had it occurred in a more severe form, might have caused death.

**Serious Adverse Event or Serious Suspected Adverse Reaction:** An adverse event or suspected adverse reaction is considered “serious” if, in the view of either the investigator or sponsor, it results in any of the following outcomes:

- Death
- A life-threatening adverse event
- Inpatient hospitalization or prolongation of existing hospitalization
- A persistent or significant incapacity or substantial disruption of the ability to conduct normal life functions
- A congenital anomaly/birth defect
- An important medical event

Important medical events that may not result in death, be life-threatening, or require hospitalization may be considered serious when, based upon appropriate medical judgment, they may jeopardize the patient or subject and may require medical or surgical intervention to prevent one of the outcomes listed in this definition

If either the IND sponsor or the investigator believes the event is life-threatening or serious, the event must be evaluated by the sponsor for expedited reporting (21CRF 312.32(a)).

**Unexpected adverse event or unexpected suspected adverse reaction:** An adverse event or suspected adverse reaction is considered “unexpected” if it is not listed in the investigator brochure or is not listed at the specificity or severity that has been observed; or, if an investigator brochure is not required or available, is not consistent with the risk information described in the general investigational plan or elsewhere in the current application, as amended.

**Expedited (Rapid) Reporting:** Certain events may require rapid notification to entities providing patient safety oversight (e.g. IRB) as detailed in [Section 10.5](#).

The categories for AE attribution to study treatment are as follows:

- Definite – clearly related
- Probable – likely related
- Possible – may be related
- Unlikely – doubtfully related
- Unrelated – clearly not related

The following definitions are from the Masonic Cancer Center's Standard Operating Procedure (SOP) Deviation Reporting:

**Major Deviation:** A deviation or violation that impacts the risks and benefits of the research; may impact subject safety, affect the integrity of research data and/or affect a subject's willingness to participate in the research. Deviations that place a subject at risk, but do not result in harm are considered to be major deviations.

**Minor Deviation:** A deviation or violation that does not impact subject safety, compromise the integrity of research data and/or affect a subject's willingness to participate in the research.

## 10.2 Event Documentation

Event monitoring and documentation begins with the 1st dose of TriKEs.

For the purposes of this study, selected expected adverse events will be assessed using the Targeted Toxicity Worksheet ([Appendix VI](#)) and any unexpected events will be collected at the following time points in relation to the GTB-3550 TriKE infusions through Day 29:

- Prior to the infusion start of each 24 hour infusion (i.e. Day 1, 2, 3, 4, and Day 8, 9, 10, 11, and Day 15, 16, 17, 18)
- At the end of the final infusion of each block (i.e. Day 5, Day 12, Day 19)
- Day 22
- Day 29

At each time point, the worst grade of the targeted toxicity since the last assessment or the previous 24 hours (whichever is shorter) will be recorded in addition to any unexpected toxicities felt at least possibly related the study treatment.

If a patient discontinues study therapy early or otherwise does not receive treatment as planned, the targeted toxicity assessment time points may be adjusted or eliminated; however, patients must be assessed for a minimum of 28 days from the 1st dose of study drug.

If a patient is not abiding by the standard of care study calendar ([Section 8.1](#)), collection of the corresponding targeted events (and research related samples) also may be altered or discontinued on an individual patient basis, as appropriate.

Monitoring for adverse events will end after the last targeted assessment; however, the investigator is obligated, upon knowledge of, to report any event meeting the criteria in [Section 10.5](#).

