#### 7.3.3 Increase in Liver Function Tests

Liver function tests will be monitored three times weekly during each CI block and at Day 22, 29, and 60 visits.

Elevated liver function tests (ALT, AST and/or total bilirubin) guidelines based on CTCAE v 5 grading:

**Grade 1 or 2:** continue therapy per protocol

**Grade 3:** discontinue treatment for the current block after completion of the currently hung infusion bag, if applicable. Missed doses are not made up.

At the time of next scheduled treatment, if LFTs return to Grade 0 in two weeks or less, initiate the next block of treatment; however, reduce the TriKE dosing by 1 dose level.

**Grade 4 or recurrence of a Grade 3:** permanently discontinue therapy

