#### **7.3.6 Cytokine Release Syndrome (CRS) or CRS-Like Symptoms**

While CRS is a clearly defined syndrome in T cell therapy, it is not known to occur to the full extent in NK cell therapies. However, we have seen immune activation syndromes with other IL-15 products that include fever, and rash. If symptoms occur, CRP, IL-6 and ferritin levels will be assessed. If indicated by the presence of medically significant symptoms and/or high IL-6 levels or any symptoms requiring intervention, steroids are the first line of treatment.

Patients will be monitored for clinical signs and symptoms of CRS through routine daily patient assessments and via the Targeted Toxicities Worksheet ([Appendix VI](#)). Refer to [Section 10](#) for the revised CRS grading system that will be used for this study.

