### **10.3 Dose Limiting Toxicity Documentation and Reporting (Phase I Dose Finding)**

The following events count toward dose limiting toxicity (DLT) during the Phase I dose finding component and must be reported the UMN Multisite Program Manager per [Section 10.6](#).

Note: DLT events are only reported for patients enrolled in the Phase I portion of the trial; however, any patient experiencing a DLT is not eligible to continue treatment per [Section 7.5](#).

A DLT is defined as a related treatment emergent toxicity that occurs within 28 days after the 1st TriKE dose with the exception of those that are clearly and incontrovertibly due to extraneous causes:

- Any Grade 4 or 5 non-hematologic events
- Grade 3 non-hematologic adverse events lasting more than 72 hours, **except** the following:
  - Non-sustained (< 7 days) Grade 3 liver function tests (ALT/AST, alkaline phosphatase, total or direct bilirubin) abnormalities in the absence of clinical signs of hepatic dysfunction (lethargy, confusion, anorexia, pruritus or tremors).
  - Non-sustained Grade 3 QTc prolongation (< 72 hours) in the absence of cardiac arrhythmia
  - Grade 3 electrolyte disturbances that resolve, with or without intervention, to < Grade 2 levels within 72 hours
  - Grade 3 fatigue
  - Grade 3 anorexia
  - Grade 3 fever
  - Grade 3 infection
- Hematologic Toxicity - Given that AML and MDS inherently leads to low neutrophils and platelets, standard grading cannot be used as many of these patients technically meet criteria for “grade 4” neutropenia or thrombocytopenia at baseline. Thus, the hematologic DLTs are listed below:
  - AML
    - Grade 4 neutrophil count (< 500/ $\mu$ L) lasting  $\geq$  29 days from start of cycle in absence of evidence of active leukemia

- Grade 4 platelet count (< 25,000/ $\mu$ L) lasting  $\geq$  29 days from start of cycle in absence of evidence of active leukemia
- Any clinically significant bleeding that is not controllable with transfusion support
- MDS/mast cell diseases:
  - Grade 4 neutrophil count (<500/ $\mu$ L) lasting  $\geq$  29 days from start of cycle in absence of evidence of active MDS/mast cell disease
  - Grade 4 platelet count (<25,000/ $\mu$ L) lasting  $\geq$  29 days from start of cycle in the absence of active MDS/Mast cell disease
  - Any clinically significant bleeding that is not controllable with transfusion support
  - Grade 4 anemia, unexplained by the underlying disease

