## Appendix VI - Targeted Expected Toxicities Worksheet

HM2015-39

CTCAE v5

Refer to [Section 10.2](#) for time points

Patient Initials: \_\_\_\_\_

Date of Assessment: \_\_\_\_\_

Assessment Time Point: \_\_\_\_\_

Toxicity	Grade 0	Grade 1	Grade 2	Grade 3	Grade 4
Infusion related reaction	None	Mild transient reaction; infusion interruption not indicated; intervention not indicated	Therapy or infusion interrupt ion indicated but responds promptly to symptomatic treatment (e.g., antihistamines, NSAIDS, narcotics, IV fluids); prophylactic medications indicated for $\leq$ 24 hrs	Prolonged (e.g., not rapidly responsive to symptomatic medication and/or brief interrupt ion of infusion); recurrence of symptoms following initial improvement; hospitalization indicated for clinical sequelae	Life-threatening consequences; urgent intervention indicated
Dyspnea	None or no change	Shortness of breath with moderate exertion	Shortness of breath with minimal exertion; limiting instrumental ADL	Shortness of breath at rest; limiting self care ADL	Life-threatening consequences; urgent intervention indicated
Hypoxia	None		Decreased O 2 saturation with exercise (e.g., pulse oximeter $<$ 88%) intermittent supplemental oxygen	Decreased oxygen saturation at rest (e.g., pulse oximeter $<$ 88% or PaO 2 $\leq$ 55 mm Hg)	Life-threatening airway compromise; urgent intervention indicated (e.g., tracheotomy or intubation)
Fever*	None	38.0 - 39.0°C (100.4 - 102.2°F)	> 39.0 - 40.0°C (102.3 - 104.0°F)	> 40.0°C (>104.0°F) for $\leq$ 24 hrs	> 40.0°C (>104.0°F) for > 24 hrs
Tachycardia*	None	Asymptomatic, intervention not indicated	Non-urgent medical intervention indicated	Medical intervention or hospitalization indicated	Life-threatening and urgent intervention indicated
Chills	None	Mild sensation of cold; shivering; chattering of teeth	Moderate tremor of the entire body; narcotics indicated	Severe or prolonged, not responsive to narcotics	

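### An expected, non-serious toxicity that is not on the Appendix VI worksheet has no stated route into the adverse-event record, even when it ends a treatment block

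*Combined protocol and SAP*

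**What the plan says.** Section 10.2 sets up two routine streams through Day 29. In the first, "selected expected adverse events will be assessed using the Targeted Toxicity Worksheet" (Appendix VI, headed "Targeted Expected Toxicities Worksheet"). The second is recorded at each time point "in addition to any unexpected toxicities felt at least possibly related the study treatment". Section 10.1 calls an event unexpected "if it is not listed in the investigator brochure or is not listed at the specificity or severity that has been observed". Section 10.2 also states: "Monitoring for adverse events will end after the last targeted assessment".

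Three further channels are set out in Sections 10.3 to 10.7: an SAE form for every serious event, a DLT form, and a stopping-rule form. On the DLT form, Section 10.3 notes that "DLT events are only reported for patients enrolled in the Phase I portion of the trial". The Phase II toxicity stopping rule in 10.4 is limited to Grade 4-5 non-hematologic, non-infectious events up to Day 42.

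Section 7.3.3 directs that, for a Grade 3 liver elevation, staff "discontinue treatment for the current block after completion of the currently hung infusion bag, if applicable". Section 7.3.6 says: "Patients will be monitored for clinical signs and symptoms of CRS through routine daily patient assessments and via the Targeted Toxicities Worksheet". Section 10 then requires an overall CRS grade on its own revised scale.

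Section 12.1 makes toxicity through Day 29 a secondary endpoint. Section 12.2 says safety will be summarised as counts and percentages and names no data source.

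**The concern.** The routine record is a closed list plus whatever is unexpected. A toxicity that the sponsor already recognises, that is not serious and that has no worksheet row falls between the two streams. The protocol itself plans for several such toxicities: liver elevation, tumor lysis and CRS have management sections, and QTc prolongation and infection are named in the DLT definition.

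The definition also works in an awkward direction. Once a toxicity is added to the investigator brochure it becomes expected and, without a worksheet row, leaves the routine record. A recognised effect of the drug would then be less visible than a surprising one.

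At stake is the secondary safety endpoint. A table built from the 10.2 data could leave out events that stopped or reduced treatment, and could lack the CRS grade that Section 10 treats as the final assessment. Dose finding is not directly affected, because it relies on the DLT form.

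**Working it through.** No sample-size or power figure is involved. The check is a count and a cross-comparison of sections.

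**Worksheet rows (Appendix VI).** The first part has 6: infusion related reaction, dyspnea, hypoxia, fever, tachycardia, chills. The second has 9: hypertension, hypotension, edema, pneumonitis, headache, confusion, rash, gait disturbance, ataxia. 6 + 9 = 15. Rows for liver tests, QTc, CRS grade, tumor lysis or infection: 0 of 5.

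**Against Section 7.3.** Infusion reaction (7.3.2), neurotoxicity (7.3.4: confusion, gait, ataxia) and pulmonary toxicity (7.3.5: dyspnea, hypoxia, pneumonitis) have rows. Tumor lysis (7.3.1), liver tests (7.3.3) and CRS as a graded syndrome (7.3.6) do not. That is 3 of 6 without a row.

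**Tracing events through the forms.** Each event is assumed to be treatment-related, non-serious and expected.

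| Event | Worksheet | Phase I DLT form | Phase II stopping-rule form | Other scheduled data |
|---|---|---|---|---|
| Grade 3 liver elevation under 7 days, no clinical hepatic signs | No row | Exempt (a) | No: Grade 3 | Laboratory |
| Grade 3 liver elevation of 7 days or more | No row | Yes | No: Grade 3 | Laboratory |
| Grade 3 QTc prolongation under 72 hours, no arrhythmia | No row | Exempt | No: Grade 3 | EKG |
| Grade 1-2 CRS as a syndrome | Components only | No: below Grade 3 | No | None for the grade |
| Grade 3 tumor lysis resolving within 7 days | No row | Not under the tumor-lysis item (b) | No: Grade 3 | Partly, from chemistry |
| Grade 3 infection | No row | Exempt | No: Grade 3, and infection is excluded | None |

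(a) Unless it also leaves the patient unable to complete one block of three infusions, which is a separate DLT item.
(b) Between 72 hours and 7 days, the general Grade 3 item could also apply.

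The second row shows the phase difference: the same event reaches a form in Phase I and none in Phase II.

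**Data that could fill part of the gap.** ALT, AST and total bilirubin are measured three times per infusion week and at Days 22, 29 and 60 (7.3.3, 8.1). EKGs are done 4 hours into each daily infusion and 4 hours after disconnection at block end (8.2). Basic metabolic panels are daily during infusions (8.1). Liver, electrolyte and QTc grades could therefore be rebuilt, though without attribution. CRS grade and infection could not.

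**Scale, by assumption only.** Section 12.3 expects about 44 patients and at most 57. Less the 30 in Phase I, that leaves 44 - 30 = 14 to 57 - 30 = 27 new Phase II patients. The documents give no rate for transient Grade 3 liver events, so a range is shown:

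| Assumed rate | 14 patients | 27 patients |
|---|---|---|
| 10% | 1.4 | 2.7 |
| 20% | 2.8 | 5.4 |
| 30% | 4.2 | 8.1 |

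**Data-entry load.** Section 10.2 lists 12 pre-infusion, 3 block-end and 2 later time points: 12 + 3 + 2 = 17. Two added rows cost at most 2 x 17 = 34 entries per patient, against 15 x 17 = 255 now.

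**The case against.** The best defence is that recording selected expected events is a deliberate choice, and that the other channels cover what matters. Much of this stands.

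- A reader might infer that the safety record holds nothing beyond the worksheet and unexpected events. The documents do not support that: SAE, DLT and stopping-rule forms exist, serious events are reported within 24 hours, and Section 8.1 schedules a toxicity assessment as late as Day 60.
- A reader might infer that the tables are bound to miss liver, QTc and CRS toxicity and so flatter the drug. That goes too far. Serious cases are captured, the scheduled laboratory and EKG data exist, and 12.2 does not confine the tables to the worksheet.
- A reader might infer that 7.3.6 sends CRS to a worksheet that cannot record it. The section speaks of signs and symptoms, and the worksheet has rows for fever, hypotension, hypoxia, tachycardia, chills and rash. What is missing is a place for the Section 10 grade.
- A reader might infer that DLT-level toxicity goes wholly unreported in Phase II. It is not reported as a DLT, but the Grade 4-5 rule and SAE reporting still apply.
- Being named in the DLT list does not make an event expected. Section 10.1 looks first to the brochure. The protocol calls the QT risk unknown in humans and doubts that full CRS occurs with NK-cell therapies. If these are unlisted, 10.2 already records them when possibly related.
- The liver counts above are not counts of dose reductions. Under 7.3.3 a reduction follows only if the tests return to Grade 0 within two weeks and a further block remains.

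The defence does not supply a stated route for the events traced above when they are expected and non-serious, nor a statement that laboratory and EKG data will feed the tables.

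**Conclusion.** The concern holds as a gap in the recording rule, not as a failure of safety reporting overall. Events that are expected, non-serious, off the worksheet, and neither a Phase I DLT nor a Phase II stopping-rule event have no stated route into the adverse-event record. The gap is wider in Phase II, and the CRS grade required by Section 10 has no named place in either phase. The Day 29 tables can under-report these toxicities; whether they would depends on the brochure and on how the analyst chooses sources.

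The documents support no figure for the number of patients affected, and the table of assumed rates is illustration only. What is firm is textual: 15 rows, 0 of 5 for the listed items, and 3 of 6 Section 7.3 toxicities without a row of their own. The point is worth acting on because it touches treatment-modifying toxicity in a secondary endpoint and is cheap to close.

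**What to change.** Three changes:

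1. In 10.2, require that any Grade 3 or higher non-hematologic event, and any event that interrupts, reduces or ends treatment, is recorded whether expected or not, in both phases.
2. In Appendix VI, add a row for CRS (Section 10 grade) and one for tumor lysis.
3. In 12.2, state that liver-test, electrolyte and QTc grades are tabulated from the scheduled laboratory and EKG data, so that they need not be entered again at all 17 worksheet time points.

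The cost is a little more data entry (at most 34 worksheet entries per patient, plus the extra event records) and some added analysis programming. No new tests or visits are needed. Lower-grade events outside these rules would remain unrecorded, in keeping with the protocol's selective approach.
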